6.5.1 Lost To Follow-Up

Patients who do not complete the scheduled 30-day follow-up clinical visit or who cannot be contacted for their 6 and 12-month telephone surveys and have not officially withdrawn from the study are considered lost to follow-up; this term does not apply to missed visits. Site personnel should make considerable effort to locate and communicate with the patient using all available methods (e.g., telephone, email and postcards). The following contact procedure is recommended at the 30-day follow-up time point:

- A minimum of 2 telephone calls on different days after discharge and over the 30-day follow-up window. This should be recorded including date, time, and site personnel initials for staff attempting to contact the patient.
- If these attempts are unsuccessful, a certified letter should be sent to the patient.
- If the patient misses two (2) consecutive scheduled contact time points and the above mentioned attempts at communicating with the patient are unsuccessful, the patient will be considered lost to follow-up.

7 STUDY PROCEDURES

7.1 Patient Evaluation Procedures

For those patients who agree to participate in the study by signing the approved Informed Consent, the following baseline examinations and tests will be performed:

- Medical History and physical examination
- 12 Lead ECG
- Administration of protocol required procedure medications
- Cardiac Biomarkers (CK, CKMB and troponin)
- Clinical Chemistry and Hematology
- Coronary Angiography

7.2 Procedure Medications

All enrolled patients receive the following protocol required medications:

Patients must receive one of the following oral ADP antagonist regimens:

- Clopidogrel 600 mg in the ER, followed by 75 mg to 150 mg per day.
- Prasugrel 60 mg in the ER followed by 5 mg to 10 mg per day.

- Ticagrelor 180 mg in the ER followed by 90 mg b.i.d.
- Ticagrelor or prasugrel is preferred to clopidogrel in patients without bleeding contraindications, according to FDA labeled instructions for use. Prasugrel (but not ticagrelor) is contraindicated in patients with prior stroke or TIA. Ticagrelor is recommended rather than prasugrel in patients <60 kg or >75 years of age.
- These loading doses must be given even if the patient is on home dual anti-platelet therapy.

Patients must also receive:

- Aspirin – 324 mg chewable aspirin given in ER prior to catheterization (regardless of earlier administration of aspirin). Alternatively, 250-500 mg IV may be administered⁵. Thereafter, 81 mg of oral aspirin per day is administered.
- Intravenous bivalirudin or unfractionated heparin (as in **Section 7.3.1** below), initiated either before or in the catheterization laboratory, but in all cases before the first balloon inflation. At operator discretion, the patient may have received unfractionated heparin prior to cardiac catheterization, and then be switched to bivalirudin in the cath lab prior to PCI as described in **Section 7.3.1** below.
- Low-flow nasal oxygen (3-5 l/min) or oxygen mask (5-10 l/min) to maintain systemic arterial pO₂ > 80 mmHg.

Use of cangrelor or glycoprotein IIb/IIIa receptor inhibitors is required prior to PCI in patients treated with only unfractionated heparin. For patients receiving bivalirudin as their procedural anticoagulant, routine use of cangrelor is allowed but use of glycoprotein IIb/IIIa receptor inhibitors is not recommended, but may be administered during the procedure if refractory thrombotic complications occur. If a GP IIb/IIIa inhibitor is used, abciximab (bolus + a 12 hour infusion) is recommended, although eptifibatide (double bolus + a 12-18 hour infusion) or tirofiban according to label is an acceptable alternative. Dosing of either should be performed per the package insert, adjusted for renal insufficiency. The IIb/IIIa inhibitor may be initiated prior to catheterization (e.g., in the emergency room), or in the cardiac catheterization laboratory prior to first balloon inflation.

The use of procedure medications will be documented on the appropriate Case Report Forms.

⁵ IV aspirin is applicable to EU sites only.

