7.3 Cardiac Catheterization Laboratory (CCL) Procedure

7.3.1 Patient Anticoagulation

Patient anticoagulation throughout the SSO₂ Therapy procedure is aligned with current practice in STEMI patients treated with primary PCI as outlined below. Bivalirudin is recommended for this study, but patient anticoagulation must consist of one of the following regimens:

- 1) Bivalirudin and cangrelor, with provisional (bail-out) use of GP IIb/IIIa inhibitors allowed
- 2) Bivalirudin, with provisional (bail-out) use of GP IIb/IIIa inhibitors allowed
- 3) Heparin and cangrelor, with provisional (bail-out) use of GP IIb/IIIa inhibitors allowed
- 4) Heparin and routine use of GP IIb/IIIa inhibitors

If bivalirudin is selected as the procedural anticoagulant, it should be administered as a bolus of 0.75 mg/kg IV prior to PCI, followed by an infusion of 1.75 mg/kg/h initiated as soon as possible. The infusion is continued at this rate through the end of SSO₂ Therapy administration and for 3-4 hours post-procedure. The infusion dose should be adjusted for renal insufficiency as per the FDA labeled Instructions for Use.

Exception: If the patient received intravenous heparin prior to cardiac catheterization (bolus or infusion), the heparin should be discontinued, and the bivalirudin should be started 30 minutes after the last dose of heparin or prior to PCI whichever occurs first. An ACT or aPTT does not need to be checked before starting the bivalirudin. In all cases the bivalirudin should be initiated before the first PCI balloon inflation or aspiration.

The use of bivalirudin is preferred but unfractionated heparin along with the routine pre-PCI use of a GP IIb/IIIa inhibitor *or* bivalirudin with the provisional (bailout) post-PCI use of a GP IIb/IIIa inhibitor may be used as the procedural anticoagulant in the IC-HOT clinical study.

If unfractionated heparin is selected, local dosing regimens may be used, although it is recommended that an initial bolus of 60 IU/kg is administered, followed by titration to the ACT of 200-250 seconds. Heparinized patients must also receive a GP IIb/IIIa inhibitor or cangrelor.

For all subjects, ACT is measured as a baseline reading prior to starting SSO₂ Therapy and after the 60-min infusion is completed. For patients receiving heparin, a 30-min ACT is also required and bolus administration of heparin to maintain ACT levels may be necessary.

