measure. 30-day cardiac MRI infarct size is often used for final infarct size measurement in clinical studies^{7,8}. Final infarct size at days 4 and 30 will be analyzed and compared to the a matched set of patients from the INFUSE-AMI trial, a study of very similar entry criteria (STEMI with proximal or mid LAD treatment) in which infarct size was assessed by cardiac MRI at the same core laboratory at the same time frame (both 4 and 30 days). Matching (1:1) will be performed on the following parameters which are known affect infarct size: Time from symptom onset to first device; baseline and post PCI TIMI flow (core laboratory); proximal vs. only mid LAD treatment; and angiographic collateral flow (if possible). In addition, since intracoronary abciximab was associated with reduced infarct size in INFUSE-AMI, these patients will be excluded from the match if possible. Attempts will be made to match all 100 SSO₂ patients. However, as the 4-day MRI was pre-specified in INFUSE-AMI in only half the patients, this may not be possible for the early time point. In this case a 2:1 match will be performed.

As an additional effectiveness analysis, the final infarct size at 30 days from the present study will be compared to the final infarct size from the SSO₂ Therapy group of the AMIHOT II study. The AMIHOT II study utilized 14-day Tc-99m sestamibi SPECT imaging for final infarct size measurement, which was the gold standard at that time. SPECT has been replaced in favor of cardiac MRI due to several reasons, including the greater ease of use and convenient collection of myocardial functional and structural data from the scans. Both techniques measure final infarct size and are validated against histological measurements^{9,10,11}.

The effectiveness comparisons are not powered, and while statistical comparisons will be reported (as described below); they are for descriptive purposes only.

Study Population for Analysis

⁷ Stone GW, Maehara A, Witzenbichler B, et al. Intracoronary abciximab and aspiration thrombectomy in patients with large anterior myocardial infarction: the INFUSE-AMI randomized trial. *JAMA* 2012 May 2;307(17):1817-26.

⁸ Carlsson M, Arheden H, Higgins CB, et al. Magnetic resonance imaging as a potential gold standard for infarct quantification. *J Electrocardiol* 2008;41(6):614-20.

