## Safety Endpoint: Objective Performance Goal

As a benchmark with a similar anterior wall AMI population, the INFUSE-AMI study yielded a 10.7% 30 day NACE event rate for control subjects receiving no aspiration and no intracoronary abciximab (control subject data analysis performed for TherOx by the INFUSE-AMI Principal Investigator [name], and the Biostatistics Department at the Cardiovascular Research Foundation). In INFUSE-AMI all of the components of the NACE endpoint were adjudicated using specific definitions, except TIMI bleeding. The same definitions will be used for the present study (except that TIMI bleeding will be adjudicated). The INFUSE-AMI study reflects current cath lab practice, and therefore the use of a composite endpoint benchmark from the control group's observed event rates is an appropriate comparator for the present prospective study.

The proposed threshold for success of the prospective trial is that the observed 30-day NACE rate in the SSO2 group will be no greater than the 30-day NACE rate observed in the INFUSE-AMI control group, 10.7%.

Furthermore, the specific 30-day NACE event categories of death, stent thrombosis, myocardial rupture, and SAE bleeding will be examined in terms of individual events. The numbers provided in **Table 4** below represent the FDA-recommended 30-day event rate guidelines for these individual safety endpoints. FDA will conduct clinical review of event counts, severity, and patient circumstances. Events will be reviewed and evaluated in the context of individual patient circumstances, relationship to the investigational device, and overall patient status in an overall determination of device safety.

**Table 4.** FDA Guidelines for Acceptable Adverse Event Rates

30-Day NACE Event	IC-HOT Trial FDA Guideline
Death	$\leq 3.0\%$
Stent Occlusion	$\leq 3.0\%$
Myocardial Rupture	$\leq 1.0\%$
TIMI Major and Minor Bleeding	$\leq 3.0\%$

Weighing the frequency, severity, and causal factors of the observed adverse events in this study, the safety profile of SSO2 Therapy will be measured against the observed effectiveness results in an overall evaluation of the risk-benefit profile.

To further evaluate the safety profile of Optimized SSO2 Therapy, the treatment cohort will be followed throughout the post-approval data collection period (12 months), however the primary endpoint will be at 30 days.

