## 2.2. Additional Study Endpoints

### Effectiveness

Effectiveness is a secondary endpoint for this study. Effectiveness data from dual time point cardiac MRI scans at day 4 and day 30 will be collected and reported, using 30-day median infarct size (% left ventricle (LV) necrosis) as the primary effectiveness outcome measure. Current practice uses 30-day cardiac MRI infarct size for final infarct size measurement in clinical studies. Final infarct size at days 4 and 30 will be analyzed and compared to the a matched set of patients from the INFUSE-AMI trial, a study of very similar entry criteria (STEMI with proximal or mid LAD treatment) in which infarct size was assessed by cardiac MRI at the same core laboratory at the same time frame (both 4 and 30 days). Matching (1:1) will be performed on the following parameters which are known affect infarct size: Time from symptom onset to first device; baseline and post PCI TIMI flow (core laboratory); proximal vs. only mid LAD treatment; and angiographic collateral flow (if possible). In addition, since intracoronary abciximab was associated with reduced infarct size in INFUSE-AMI, these patients will be excluded from the match if possible. Attempts will be made to match all 100 SSO2 patients. However, as the 4-day MRI was pre-specified in INFUSE-AMI in only half the patients, this may not be possible for the early time point. In this case a 2:1 match will be performed.

As an additional effectiveness analysis, the final infarct size at 30 days from the present study will be compared to the final infarct size from the SSO2 Therapy group of the AMIHOT II study. The AMIHOT II study utilized 14-day Tc-99m sestamibi SPECT imaging for final infarct size measurement, which was the gold standard at that time. SPECT has been replaced in favor of cardiac MRI due to several reasons, including the greater ease of use and convenient collection of myocardial functional and structural data from the scans. Both techniques measure final infarct size and are validated against histological measurements.

---

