#### **6.5.3. Index PCI, SSO2 Therapy, Core Lab Variables, and MRI**

Tabulations for the index PCI procedure, hemodynamics, and pre-screening ABG and ACT, and procedural medications will be provided. PCI procedure variables will include the guide catheter and femoral arterial sheath sizes, presence of multi-vessel disease, target lesion characteristics, pre-and post-procedure TIMI flow and % stenosis, presence of dissection, number of stents, total stented length, stent type and complications.

SSO2 Therapy procedure data, including arterial access variables, device usage information, intra-procedural data, including HR, BP, arterial blood gas measurements and ACT values, and post-therapy data will be presented descriptively.

By-subject listings will include the reference data for these tables.

The Angiographic Core Lab values tabulations include pre-PCI angiographic data, post thrombectomy prior to stent angiographic data, pre-stent and post-stent worst angiographic data, post-PCI prior to SSO2 angiographic data, angiographic quantitative measurements, post-SSO2 angiographic data, and vessel level characteristics.

Tabulations for thromboembolic complications will be provided.

By-subject listings will include the reference data for these Core Lab tables.

Tabulations for compliance to the scheduled cardiac MRI scans for all patients and for only in-time window patients will be provided. Cardiac MRI Core Laboratory data will be tabulated for all patients for only in-time window patients and for all patients with paired MRI scan data (i.e., both 3-5 day and 30 day MRI data).

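### The infarct-size match removes intracoronary abciximab from the INFUSE-AMI side only, leaves GP IIb/IIIa use in IC-HOT unmatched, and does not address aspiration on either side

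*Protocol*

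**What the plan says.** **The match.** Protocol 9.2 and SAP 2.2 (Effectiveness) compare infarct size with a matched set from INFUSE-AMI. The matching variables are "Time from symptom onset to first device; baseline and post PCI TIMI flow (core laboratory); proximal vs. only mid LAD treatment", plus collateral flow if possible. On abciximab, Protocol 9.2 says "since intracoronary abciximab was associated with reduced infarct size in INFUSE-AMI, these patients will be excluded from the match if possible"; SAP 2.2 repeats this. Neither section mentions GP IIb/IIIa use or aspiration as a matching variable, or restricts the IC-HOT patients on either.

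**GP IIb/IIIa inhibitors in IC-HOT.** Protocol 7.3.1 permits four regimens. One is heparin with routine GP IIb/IIIa inhibition; the other three allow these agents as bail-out. Bivalirudin is preferred. When an agent of this class is given, Protocol 7.2 states: "If a GP IIb/IIIa inhibitor is used, abciximab (bolus + a 12 hour infusion) is recommended". The route of the bolus is not given.

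**Aspiration in IC-HOT.** Protocol 7.3.1 foresees it: "In all cases the bivalirudin should be initiated before the first PCI balloon inflation or aspiration". SAP 6.5.3 tabulates "post thrombectomy prior to stent angiographic data".

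**The safety benchmark.** The 10.7% NACE goal comes from a different INFUSE-AMI group: "control subjects receiving no aspiration and no intracoronary abciximab" (SAP 2.1; n = 112 in Protocol 9.2).

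**Status.** Thirty-day median infarct size is the primary effectiveness measure. The comparisons are unpowered and descriptive. Protocol 9.2 and SAP 2.1 nevertheless weigh the safety profile against the effectiveness results in an overall risk-benefit evaluation.

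**The concern.** The plan treats intracoronary abciximab as a determinant of infarct size, giving as its reason "since intracoronary abciximab was associated with reduced infarct size in INFUSE-AMI", and then controls it in one of the two groups. A co-treatment that affects infarct size and differs in frequency between the groups shifts the observed difference, and that shift would be read as part of the SSO2 effect.

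Aspiration is the other factor randomised in INFUSE-AMI, as the design paper cited in SAP 2.1 describes (a 2 × 2 factorial). It was considered important enough to remove from the NACE benchmark, yet the infarct-size match does not mention it, and the plan does not say why the two comparators differ.

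This matters because the INFUSE-AMI match is the only planned infarct-size comparison with patients not given SSO2. The other comparison is with the SSO2 group of AMIHOT II.

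**Working it through.** The plan gives no effect size, SD or power for this comparison, so there is no stated figure to reproduce. The check has two parts.

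**1. The rules side by side**

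| Co-treatment | INFUSE-AMI side of the match | IC-HOT side of the match |
|---|---|---|
| Intracoronary abciximab | Removed, if possible | No rule |
| GP IIb/IIIa inhibitor, other route or agent | No rule | No rule; routine in one regimen, bail-out in three |
| Aspiration | No rule | No rule; foreseen and tabulated |

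Only the first row is handled on one side. The restriction to patients without aspiration applies to the NACE benchmark, not to the infarct-size match.

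**2. How large the shift could be**

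Let pT be the share of IC-HOT patients co-treated, pC the share of matched controls co-treated, and d the reduction in infarct size from the co-treatment, in points of % LV. The shift in the difference in means is

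B = (pT − pC) × d,

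with positive B a spurious benefit for SSO2. The plan reports medians, so this is a guide to scale only. The documents give none of the three inputs; every value below is an assumption.

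*Abciximab.* Set pC = 0 (the exclusion fully achieved) and suppose that abciximab in IC-HOT acts like the excluded intracoronary use:

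| d | pT = 10% | pT = 50% |
|---|---|---|
| 1 | 0.10 × 1 = 0.1 | 0.50 × 1 = 0.5 |
| 2 | 0.10 × 2 = 0.2 | 0.50 × 2 = 1.0 |
| 5 | 0.10 × 5 = 0.5 | 0.50 × 5 = 2.5 |

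*Aspiration.* Set pC = 0.5 (equal allocation in the factorial, no exclusion) and d = 2:

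- pT = 10%: (0.10 − 0.50) × 2 = −0.8
- pT = 50%: (0.50 − 0.50) × 2 = 0
- pT = 100%: (1.00 − 0.50) × 2 = +1.0

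The reference is the 5-point absolute median reduction that Protocol section 2 calls clinically meaningful. The abciximab term is positive here only because pC was set to zero and an intracoronary-type effect was assumed. The aspiration term can take either sign.

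**The case against.** A reader might infer that the plan tilts the comparison toward SSO2 by clearing both abciximab and aspiration from the controls while leaving both in the treated group. The documents do not support that.

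- **Aspiration is not cleared from the controls in this match.** Retained INFUSE-AMI patients may have been aspirated.
- **The plan's premise covers the intracoronary route only.** Protocol 7.2 describes a bolus and a 12-hour infusion, and allows the agent to be started before catheterisation, for example in the emergency room. Such a start is not intracoronary. No section provides for intracoronary dosing; that none forbids it is an argument from silence.
- **Control exposure to systemic GP IIb/IIIa inhibitors is unknown.** If it exceeds that in IC-HOT, any effect would work against SSO2. The exclusion itself is qualified ("these patients will be excluded from the match if possible"), so some intracoronary use may remain among controls.
- **Use in IC-HOT may be low.** Bivalirudin is preferred, and with it these agents are not recommended except for refractory thrombotic complications. Patients who receive bail-out treatment need not have smaller infarcts.

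These points stand, and they remove any claim about direction. Three further defences carry less weight.

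- SAP 6.4 lists use of IIb/IIIa inhibitors as a covariate, but only as one that may be included in exploratory work. It is not tied to the match, and aspiration is not listed.
- Matching on post-PCI TIMI flow may absorb part of an effect, but it is not a record of the co-treatment.
- The comparison is descriptive, which limits the consequence; an unpowered comparison can still be confounded.

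Different comparators for safety and effectiveness can also be a legitimate choice. With 112 patients in the group without aspiration or intracoronary abciximab, and a wish to match 100 on several variables, restricting to that group would leave little room. That argues for adjusting for aspiration rather than excluding it.

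**Conclusion.** The point holds in a limited form. The abciximab rule applies to one group only, GP IIb/IIIa use in IC-HOT is neither matched nor restricted, and aspiration is unaddressed on both sides. The comparison can therefore be confounded by co-treatment.

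Neither the size nor the direction can be determined. The ranges of 0.1 to 2.5 points for abciximab and −0.8 to +1.0 for aspiration rest on assumed prevalences and effects, and the first also on an intracoronary-type effect that the documents do not attribute to IC-HOT dosing. All are below the 5-point reference. Study success rests on NACE and is unaffected. What is exposed is the effectiveness side of the risk-benefit evaluation. A change is worthwhile because it is cheap.

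**What to change.** In SAP 2.2:

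1. Apply the intracoronary-abciximab exclusion to both groups in the matched analysis.
2. Pre-specify a sensitivity analysis of 30-day infarct size in the matched set, adjusted for GP IIb/IIIa use started before SSO2 (yes/no) and aspiration thrombectomy during the index PCI (yes/no). Controls receive no SSO2, so define a parallel cut-off for them; completion of the index PCI is the natural one.
3. Do not adjust for GP IIb/IIIa use started during or after SSO2. Protocol 7.3.1 allows bail-out use after PCI and SAP 2.1 foresees stent thrombosis during SSO2 delivery, so later use could be a consequence of SSO2.
4. Confirm that the procedure-medication CRF captures the route and timing of any GP IIb/IIIa bolus, and that the INFUSE-AMI data hold the corresponding items. The CRFs are in Protocol Appendix A, which was not available here.

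The cost is slightly more analysis and possibly a few lost pairs. Procedure medications and post-thrombectomy angiography are already recorded. No treatment rule changes.

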7.3 Cardiac Catheterization Laboratory (CCL) Procedure

7.3.1 Patient Anticoagulation

Patient anticoagulation throughout the SSO₂ Therapy procedure is aligned with current practice in STEMI patients treated with primary PCI as outlined below. Bivalirudin is recommended for this study, but patient anticoagulation must consist of one of the following regimens:

- 1) Bivalirudin and cangrelor, with provisional (bail-out) use of GP IIb/IIIa inhibitors allowed
- 2) Bivalirudin, with provisional (bail-out) use of GP IIb/IIIa inhibitors allowed
- 3) Heparin and cangrelor, with provisional (bail-out) use of GP IIb/IIIa inhibitors allowed
- 4) Heparin and routine use of GP IIb/IIIa inhibitors

If bivalirudin is selected as the procedural anticoagulant, it should be administered as a bolus of 0.75 mg/kg IV prior to PCI, followed by an infusion of 1.75 mg/kg/h initiated as soon as possible. The infusion is continued at this rate through the end of SSO₂ Therapy administration and for 3-4 hours post-procedure. The infusion dose should be adjusted for renal insufficiency as per the FDA labeled Instructions for Use.

Exception: If the patient received intravenous heparin prior to cardiac catheterization (bolus or infusion), the heparin should be discontinued, and the bivalirudin should be started 30 minutes after the last dose of heparin or prior to PCI whichever occurs first. An ACT or aPTT does not need to be checked before starting the bivalirudin. In all cases the bivalirudin should be initiated before the first PCI balloon inflation or aspiration.

The use of bivalirudin is preferred but unfractionated heparin along with the routine pre-PCI use of a GP IIb/IIIa inhibitor *or* bivalirudin with the provisional (bailout) post-PCI use of a GP IIb/IIIa inhibitor may be used as the procedural anticoagulant in the IC-HOT clinical study.

If unfractionated heparin is selected, local dosing regimens may be used, although it is recommended that an initial bolus of 60 IU/kg is administered, followed by titration to the ACT of 200-250 seconds. Heparinized patients must also receive a GP IIb/IIIa inhibitor or cangrelor.

For all subjects, ACT is measured as a baseline reading prior to starting SSO₂ Therapy and after the 60-min infusion is completed. For patients receiving heparin, a 30-min ACT is also required and bolus administration of heparin to maintain ACT levels may be necessary.

Intravenous cangrelor may also be used according to label per investigator discretion, administered as a bolus plus infusion, with the infusion continued for 2-4 hours post-PCI. For patients receiving bivalirudin, cangrelor may be administered in the same IV.

